##### **Metabolic health:**

Any changes in fasting blood glucose, HbA1c, total cholesterol, HDL- and LDL-cholesterol, triglycerides, immune cells and glucose lowering medication use determined at t = 0 (month 0; baseline visit), t = 3 (month 3, first investigational visit), t = 6 (month 6; second investigational visit) and t = 12 (month 12; third investigational visit (end of the trial)).

### **Body composition:**

Any changes in height, weight, waist- and hip-circumference and any changes in body composition with regard to muscle- / fat mass with the use of bio electrical impedance measurements, determined at t = 0 (month 0; baseline visit), t = 3 (month 3, first investigational visit), t = 6 (month 6; second investigational visit) and t = 12 (month 12; third investigational visit (end of the trial)).

### **Quality of life**

Any changes in quality of life with use of the SF-36 questionnaire, determined at t = 0 (month 0; baseline visit), t = 3 (month 3, first investigational visit), t = 6 (month 6; second investigational visit) and t = 12 (month 12; third investigational visit (end of the trial)).

### **Depressive symptoms PHQ 9**

Any changes in quality of life with use of the PHQ9 questionnaire, determined at t = 0 (month 0; baseline visit), t = 3 (month 3, first investigational visit), t = 6 (month 6; second investigational visit) and t = 12 (month 12; third investigational visit (end of the trial)).

### **Physical functioning**

Any changes in handgrip strength and timed chair-stand test with use of the JAMAR Hydraulic Handdynamometer (SEHAN Corp. Korea- Biometrics Europe BV, Almere) determined at t = 0 (month 0; baseline visit), t = 3 (month 3, first investigational visit), t = 6 (month 6; second investigational visit) and t = 12 (month 12; third investigational visit (end of the trial)).

### **6.1.3 Other study parameters**

Individual patient characteristics: age, sex, ethnicity, level of education, employment status, medical history and medication use.

A process evaluation of LiPAT will give insight into the reach, implementation, and satisfaction of the intervention program. Research questions for the process evaluation are:

- Who participated in the intervention and who dropped out?
- Was the intervention executed as planned?
- How did participants experience the intervention and specifically the workshops and the use of Fitbit inspire and the mobile application?

A partially structured interview at the end of the intervention (month 6) with all participants and the research nurse will be carried out to capture their experiences with LiPAT. The following aspects will be covered during the interviews; some items are only relevant for the intervention group (e.g. the use of the Fitbit inspire). This process evaluation is based upon Moore, GF et al. BMJ 2015.

Dose delivered (for the intervention and control group)

1. Extent to which the research nurse:
  - a. informed the participant about the risks of a sedentary lifestyle and the benefit of LiPA
  - b. collaboratively set goals and set up an action plan with the participant
  - c. gave feedback based on the general physical activity goals
  - d. discussed with the participant barriers and facilitators for being active

Fidelity

1. Extent to which LiPAT was implemented as planned by the participant?
2. Have the participant and research nurse perceived any technical problems with the Fitbit inspire device? (for intervention group only)
3. Have the participant and research nurse experienced any technical problems with the mobile application? (for intervention group only)

Dose received (exposure)

1. Overall opinion of the participant regarding engagement in the intervention program
2. Instruction of the Fitbit inspire and the mobile application (use of the manual and the instruction)(for intervention group only)

Dose received (satisfaction)

1. Experience with LiPAT
  - a. Activity monitoring
  - b. Workshops
  - c. Feedback messages
2. Experience with the mobile application (for intervention group only)
  - a. Goal setting
  - b. Activity monitoring
  - c. Feedback messages

3. How satisfied were the participants and the research nurse with the intervention program – workshops and LiPAT?
4. How did the participants perceive the outcomes and relevance of the interventions?

- Furthermore, the remainders of the blood samples after quantification of the primary laboratory values will be stored in a biobank for future determination of (bio)markers that might be associated with physical activity. For any such future procedures further approval will be sought from the METC/MUMC+. In addition we will ask the participants for their specific approval to share / use their data with third parties for scientific valorization purposes only.

### **6.2 Randomisation, blinding and treatment allocation**

Randomisation by the research staff will take place during the baseline visit (please see above) with / via block randomization in a block size of 4 (Suresh, KP. J Hum Reprod Sci. 2011).

Participants will be randomly assigned in Ldot, a web-based tool, designed to monitor study logistics, to the LPA intervention group or the control group.

Randomisation will be stratified according to sex to ensure an equal distribution of men and women in both groups.

This is a single-blind design. To ensure blinding, participants will be instructed to not discuss their assigned intervention during any of the trial visits with the research nurse or vascular technician performing any of the trial measurements.

The participants in the intervention group will be asked not to wear their Fitbit inspire device on trial visit days and will be reminded not to do so via the web interface.

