### **3. STUDY DESIGN**

This study is a single-blinded randomized controlled trial (enrollment via block randomization (block size of 4)). The duration of the study is 12 months; a 6-month intervention with a 6 month follow-up period to examine both the long-term health effects of the intervention as well as any long-term compliance to the intervention.

Study measurements of all participants will take place at baseline (month 1 (t = 0)), month 3 (t = 3), month 6 (t = 6), and month 12 (t = 12) at the Maastricht UMC+.

Participants in the intervention group will be instructed to increase their LiPA by decreasing sedentary time. Participants will follow 4 workshops in group sessions on strategies to change their behaviour and will receive a feedback physical activity monitor that will be worn continuously on the wrist and provide e-feedback on activity behaviour. During the COVID-19 crisis the workshops temporarily are offered online. The intervention procedures are described in more detail in section 5.

Participants in the control group will receive 4 workshops in group sessions on healthy lifestyle including information and strategies to increase LiPA and reduce sedentary time similar to the intervention group, but will not receive a feedback-activity monitor.

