### 3.1 Duration

The total duration of the study is 3 years. The duration of the RCT is 12 months.

The intervention period is 6 months with a 6-month follow-up.

Expected starting date for the study: quarter 4, 2016

Expected starting date for enrolment participants: quarter 1, 2017

Expected date finished enrolment participants: quarter 1, 2018

Expected date end of follow-up: quarter 1, 2019

Statistical analyses and report of the results: quarter 3, 2019

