#### Screening

A preliminary screening will be carried out by telephone interview in order to decide whether the participant is eligible for the study (see section 4.2 and 4.3 for the in- and exclusion criteria). The participant will then be invited for the baseline visit, which starts with the informed consent procedure (please see appendices for informed consent) and an explanation of this very first baseline visit. The baseline namely consists of two parts. Part A is strictly part of the inclusion procedure. During this part a standard physical examination will take place and an ultrasound scan will be performed to screen for large atherosclerotic plaques of the carotid arteries (see below). If then the participants is indeed eligible part B will take place in which the investigational baseline measurements are performed. After the above procedure randomization will take place. From then on participants will run through the protocol either being part of the intervention or control group.

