### Overview of workshop contents:

#### Intervention group

Workshop 1 – month 1 (duration 2 hours)

Topics to be covered:

- the health risks of sedentary behaviour
- what is LiPA and what are the health benefits
- what are generic strategies to increase LiPA by reducing sedentary time
- introduction of the Fitbit inspire and the mobile application
- individual goal setting

Workshop 2 – month 2 (duration 1 hour)

- physical activity and a healthy lifestyle in type 2 diabetes; therapeutic benefits
- reflection of participants on their LiPA levels
- experience with the Fitbit inspire and the what is LiPA and how can it be increased
- activity levels and change in the workshop group (comparing participants' progress (anonymized))
- individual goal setting

Workshop 3 – month 3 (duration 1 hour)

- activity levels and change in the workshop group (comparing participants' progress (anonymized))
- group discussion on progress and discuss strategies to increase LiPA

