## **10. ADMINISTRATIVE ASPECTS, MONITORING AND PUBLICATION**

### **10.1 Handling and storage of data and documents**

Study data will be entered in Castor (<https://www.castoredc.com/>) a save cloud based electronic data capture platform that is supported by MEMIC. At the end of the study data can be exported for analyses. The central database consists of two separate components: Section 1 contains personal information on the participants entered in Idot and is physically separate from the research results. This section records and stores a participant's ID and personal information, such as name, address and contact information. This section is also responsible for monitoring consent forms. The file does not contain research information and capable of meeting the logistical requirements.

Section 2 contains the research results (Castor) with the corresponding participant-specific ID code and is only accessible to the investigational team. This file contains all registered research results such as questionnaire data, physical examination information and imaging research. It also records which researcher conducted the measurements and whether any adjustments were made. The key to the ID code will be under the charge of the principal investigators of LiPAT. Data will be stored in this fashion for 15 years after the end of the study. We state explicitly that the following parties will have access to the data next to all primary investigators of LiPAT themselves, governmental parties from the ministry of Health (e.g., Inspectie voor de Gezondheidszorg (or others if obliged to do so by law)), trial monitors (e.g, CTCM) and METC-members.

With regard to the remainders of the blood samples after determination of the primary laboratory variables, these will be stored, under their ID-code, in a MUMC+ owned biobank for a period of 15 years after the end of the study.

We state explicitly that the following parties will have access to the biodata next to all primary investigators of LiPAT themselves, governmental parties from the ministry of Health (e.g., Inspectie voor de Gezondheidszorg (or others if obliged to do so by law)), trial monitors (e.g, CTCM) and METC-members.

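### A single printed block size of 4 within sex makes the end of each block deducible to anyone who knows the earlier assignments; varying, withheld sizes would be a cheap improvement

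*Protocol*

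**What the plan says.** Protocol section 6.2 assigns participants "with / via block randomization in a block size of 4" and stratifies by sex. Section 3 gives the same size: "enrollment via block randomization (block size of 4". No other size is mentioned, and nothing says that the size is withheld from any staff. All visits are at one centre.

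On who randomises and when, section 6.2 states: "Randomisation by the research staff will take place during the baseline visit". Under Screening in section 3.2, that visit has two parts. Part A (physical examination and carotid ultrasound) still decides eligibility, and Part B collects the baseline measurements. Only then: "After the above procedure randomization will take place". Section 9.2 repeats this order.

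The assignment is made in a web-based logistics tool. Section 10.1 describes how the data are divided: "Section 1 contains personal information on the participants entered in Idot and is physically separate from the research results". That separates identities from results. It does not say who can see assignments already made.

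Section 8.1 uses baseline PWV and sex as covariates in the analysis of PWV.

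**The concern.** Blocking protects balance at the price of predictability. With one known size, block boundaries need no inside information: count the men in fours and the women in fours. A member of staff who also knew the arms already given in the current block would know the last arm before it is issued, and sometimes the last two.

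This matters because the next participant's eligibility is still open at the baseline visit. Several exclusion criteria in section 4.3 call for judgement, such as severe joint complaints or uncontrolled diabetes. Knowledge of the coming arm at that moment opens a route to selective inclusion, which randomisation is meant to close.

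**Working it through.** The protocol gives no predictability figure, so there is none to reproduce.

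**Inputs.** Block size 4 (sections 3 and 6.2); 160 participants, 80 per group (Summary, section 4.4), so 2 + 2 in each block; two strata by sex (section 6.2); enrolment expected from quarter 1, 2017 (section 3.1) until "Expected date finished enrolment participants: quarter 1, 2018", taken as about 12 months.

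**Worst case: every earlier assignment known at once.** An arm is certain when the other arm has used both its places. The six equally likely orderings give:

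| Ordering | Certain places |
|---|---|
| AABB, BBAA | 3rd and 4th (2 each) |
| ABAB, ABBA, BAAB, BABA | 4th only (1 each) |

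- Certain places: 2 × 2 + 4 × 1 = 8 of 24 = 1/3.
- Expected count: 160 × 1/3 = 53.3.
- Over 40 full blocks the count is 40 + Binomial(40, 1/3). The SD is √(40 × 1/3 × 2/3) = 2.98, the central 95% range is 48 to 59, and the possible range is 40 to 80.
- Incomplete last blocks, over every possible split of 160 between the sexes, change the expectation only to between 52.0 and 53.3.

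**Best guess.** Naming the arm with more places left is right with probability 1/2, 2/3, 2/3 and 1 at places 1 to 4. The mean is 2.833/4 = 70.8%.

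**Partial knowledge (assumption).** Suppose each earlier assignment is known independently with probability q. A place is then certain only if both members of the used-up arm are known, so the share is q²/3.

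- q = 0.75: 160 × 0.5625/3 = 30.
- q = 0.5: 160 × 0.25/3 = 13.3.
- q = 0.25: 160 × 0.0625/3 = 3.3.

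**Delayed knowledge (assumption).** Simulation with arrivals spread evenly, sexes 50:50 and each arm known only after a fixed delay. Expected certain allocations of 160:

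| Enrolment period | 7 days | 14 days | 30 days |
|---|---|---|---|
| 9 months | 9.9 | 1.8 | 0.0 |
| 12 months | 15.5 | 4.2 | 0.1 |
| 15 months | 19.7 | 7.1 | 0.6 |
| 36 months | 35.6 | 23.8 | 8.7 |

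**Varying blocks, all past arms known.** Simulation with two strata of 80 and equally likely sizes; the observer knows the set of sizes but not their order.

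| Sizes | Certain | Best guess right |
|---|---|---|
| 4 fixed | 33.3% | 70.8% |
| 4 and 6 | 5.5% | 69.2% |
| 4, 6 and 8 | 2.26% (3.6 of 160) | 67.8% |

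A 104/56 split of the sexes with 4, 6 and 8 gives 2.33% and 67.9%.

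**The case against.** The strongest reply is that no section describes the observer behind the figure of 53. That person must learn every assignment at once, follow each sex separately and influence inclusion. This stands: a reader might infer that about 53 allocations would be foreseen in this trial, and the protocol does not support that. Who can see assignments is often settled in system set-up or delegation records, so silence on it is not itself a fault.

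There are also safeguards:

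- Assignment is made in a web tool, after consent, eligibility and baseline measurements.
- Participants contact the team themselves, and many criteria are numeric or checkable.
- Section 9.2 gives the consent procedure and physical examination to the principal investigator, while section 6.2 has research staff randomise. The sentence in 9.2 ends at a removed name, so the division of roles cannot be read in full.
- Adjustment for baseline PWV and sex would absorb part of any prognostic imbalance caused by selection.

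These lower the risk. None of them stops the last place of a block from being deduced, and covariate adjustment cannot correct for unmeasured differences.

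It is also fair to say that a fixed block of 4 is a legitimate design with tight balance, and that varying sizes barely change guessing. What they remove is certainty.

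Two further inferences should be resisted. The activity monitor does not reveal arms at randomisation: workshop 1, in month 1, is where section 5.1 places the "introduction of the Fitbit inspire and the mobile application". And the term research nurse, used in section 6.1.3 for a person who sets goals with participants, does not show that a blinded assessor is unblinded. Section 6.2 defines the blinded role by function, as the "research nurse or vascular technician performing any of the trial measurements", and nothing says that one person does both. That is at most a matter of wording.

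**Conclusion.** The point holds as a cheap improvement to the randomisation procedure, not as evidence of bias. A single, disclosed block size of 4 within a visible stratum makes on average at most one allocation in three certain (53 of 160), given complete and immediate knowledge of earlier assignments. With partial or delayed knowledge the number is far smaller, and near zero if arms become known a month late under the planned 12-month enrolment. Where this trial lies in that range cannot be told from the protocol. The probabilities q, the delays and the even rate of enrolment are assumptions. No bias in PWV has been estimated.

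**What to change.** For blocks not yet started in each sex stratum, generate the list with randomly varying sizes, for example 4, 6 and 8. Withhold the sizes from staff who enrol or measure, and delete the figure from sections 3 and 6.2.

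Costs: an amendment handled under section 10.3, and a change to the allocation list. The protocol does not describe the tool's randomisation options, so whether it supports varying sizes must be checked. An incomplete last block can leave an imbalance of up to half its size, so the possible imbalance per stratum rises from 2 to 4 (4 to 8 over both sexes); the simulated mean with 4, 6 and 8 is about 0.6 per stratum. Sizes of 4 and 6 would cap it at 3, with 5.5% of allocations certain in the worst case.

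The change helps only future blocks. Enrolment was expected to end in quarter 1, 2018, and section 8.1 already deals with COVID-19 delays, so it may be complete. In that case, report the fixed, disclosed block size as a limitation.

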### **6.3 Study procedures**

Investigational visits will be carried out at t = 0 (month 0; baseline visit), t = 3 (month 3, first investigational visit), t = 6 (month 6; second investigational visit) and t = 12 (month 12; third investigational visit (end of the trial)).

The investigational visits will consist of:

### **Arterial Stiffness measurements**

Aortic pulse wave velocity (aPWV): i.e., carotid to femoral pulse wave velocity) will be determined with the use of applanation tonometry according to recent guidelines [25]. In brief, pressure waveforms will be determined at the right common carotid and right common femoral arteries. The difference in the time of pulse arrival from the R-wave of the electrocardiogram between the two sites will be calculated with an intersecting tangents algorithm. The pulse wave travel distance will be calculated as 80% of the direct straight distance (measured with an infantometer) between the two arterial sites. aPWV will then be calculated as the median of three consecutive aPWV recordings (defined as travelled distance/transit time).

Carotid arterial stiffness will be determined at the left common carotid, with the use of an ultrasound scanner equipped with a 7.5-MHz linear probe (MyLab 70, Esaote Europe B.V., Maastricht, the Netherlands) together with a dedicated PC-based acquisition system (ART.LAB, Esaote Europe B.V. Maastricht, the Netherlands).

This setup enables the measurement of diameter, distension and intima-media thickness as described previously [6].

From these data carotid distensibility will be determined. All arterial ultrasound measurements will be analysed off-line in a blinded fashion.

For the above procedures theoretically a risk of stroke exists in case of the presence of carotid plaques. Manipulation of these plaques may theoretically cause stroke. Yet, the risk of plaque rupture during ultrasonography can be considered small as in accordance with standard practice no pressure should be applied to the skin in order to execute these measurements reliably. With regard to tonometry, this risk can be considered somewhat higher as this procedure requires the application of a certain amount of pressure to a relatively small area of the carotid artery wall via the tonometer. Despite the fact that none of the international guidelines on arterial ultrasonography and tonometry have noted warnings in their guidelines with regard to this issue LiPAT will withdraw participants with severe carotid atherosclerotic plaques from the study. A severe carotid plaque is identified by an IMT thickness  $\geq 5$  mm in addition to both in longitudinal and transversal images into the

lumen protruding wall structures. The vascular technician will bring such a participant to the attention of the principal investigator whom will present such a participant to the department of neurology for further examination.

### Microcirculation Measurements

Funduscopy will be performed to examine the participant's retinal microcirculation.

Measurements will take place in a sitting position at dim light. Subjects will be asked to take off their glasses or contact lenses prior to the measurements, to hold still, and to look straight ahead while making photos of the retina. We will not use mydriasis. In total, we will take six photos, three for each eye using a Funduscope (Non-Mydriatic Auto Fundus Camera, Model AFC-230, NIDEK). In order to get a total image of the fundus of a participant's eye, photos will be taken from different angles with 30 seconds interval. The retina and its corresponding visual field can be divided into quadrants. Figure 1 provides an indication of the analysed quadrants, namely quadrant 1M (pupil central), quadrant 2 (macula central), and quadrant 3M (temporal). This measurement is similar to that performed at the hospital's outpatient clinic, and there are no risks associated with funduscopy.

[figure not shown]

Figure 1. Fundus photograph indicating the different quadrants.

Skin laser Doppler flowmetry: during the macrovascular measurements, flowmotion of skin microcirculation will be evaluated by laser Doppler flowmetry (Periflux 5000, Perimed Sweden). The probe is applied to the wrist of the left arm. In addition, heat-induced vasodilation – endothelium-dependent – of the skin microcirculation is evaluated with a second laser Doppler probe inducing local heating to 44°C during 25 minutes. Participants will not notice the recording of the laser Doppler signal, nor will they notice the local heating.

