## 2. OBJECTIVES

### Primary Hypothesis:

A LiPA intervention program based upon increasing LiPA by replacing sedentary time (approx. 1 hour) is effective in a) lowering arterial stiffness as estimated by aortic PWV and carotid distensibility and b) enhance microvascular function as estimated by retinal photos and skin heat-induced hyperemia in individuals with T2D.

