Participants in the intervention group will receive a feedback physical activity monitor (Fitbit inspire; commercially available consumer product (<https://www.fitbit.com/inspire>)). Participants will receive extensive instructions on its use, the internet interface and how it will provide feedback during the first group workshop. The Fitbit inspire is worn on the wrist like a wristwatch. It has a watch interface and it tracks movement tri-axially. The data is synchronized with the mobile phone app, with a protected cloud-based platform that collects and analyses data from the device. The app is designed to help the participant to self-monitor their physical activity levels and includes information on total activity, number of steps, kcals burned, and sleep parameters. Based on the collected data the investigators will be able to provide personalised recommendations to the participants with the use of

proprietary algorithms on activity levels and activity goals can be set. After the first week of data collection, information about participants' average activity is available which will be used to set an activity goal. This goal will be adjusted accordingly during the trial. For example if a participant has on average 4 hours of activity a day, a goal of 4,5 hour of activity a day could be set as an activity goal.

Furthermore, participants will be alerted automatically during the day (from 0800 to 2100 hrs) when he/she has been inactive for prolonged periods of time (based on an activity goal of 250 steps per hour). This should remind the participant to engage in LiPA.

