Participants will be instructed to wear the activity monitor continuously, also during the night, to be able to monitor sleeping behaviour. Participants are advised only to take the device off when the battery has to be recharged. Data will be automatically transferred by Bluetooth to the mobile application and the protected cloud-based platform and internet interface so that the participant can monitor progress and, if so required additional e-feedback can be dispersed. If LiPA goals are met, participants will be automatically rewarded by means of positive (e-)reinforcement (e.g., by encouragement messages in the app ("Well done! You have met your LiPA goal!") and encouragement symbols (e.g., a smiley). There will be no negative messages dispersed to the participant if LiPA goals are not met. During the intervention, small (digital) prizes for encouragement (e.g. fruit basket or a digital "thumbs up") will be raffled among participants who reach their activity goals.

During the first month of the intervention, participants will get acquainted with the use of the Fitbit inspire and bi-weekly phone calls with participants are planned to monitor use of the feedback activity monitor and set LPA goals based on their habitual activity. After this run-in period, monthly phone calls with participants are planned during the second and third month to provide feedback on the Fitbit inspire use and to help participants to reach their LiPA goals with the use of the watch and web-based interface. As from month 4 onwards, no structural phone calls with participants are planned anymore and feedback rests entirely upon the digital platform as by choice of the participant. During the complete period of the intervention a manned help-desk is available for any questions by the LiPAT participants.

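### The wrist for the intervention arm's monitor is not fixed, so skin laser Doppler at the left wrist may be recorded on recently strapped skin in one arm only

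*Protocol*

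**What the plan says.** **Measurement site.** Section 6.3 (Microcirculation Measurements) describes a laser Doppler recording of skin flowmotion: "The probe is applied to the wrist of the left arm". Heat-induced vasodilation "is evaluated with a second laser Doppler probe inducing local heating to 44°C during 25 minutes". No separate site is given for this second probe.

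**Device.** Section 5.1 gives the intervention arm a feedback monitor: "The Fitbit inspire is worn on the wrist like a wristwatch". It also says "Participants will be instructed to wear the activity monitor continuously, also during the night, to be able to monitor sleeping behaviour", and "Participants are advised only to take the device off when the battery has to be recharged". Under the Control group heading, section 5.1 says that controls get no such device.

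**Visit days.** Section 6.2: "The participants in the intervention group will be asked not to wear their Fitbit inspire device on trial visit days". Participants are reminded of this through the web interface and told not to discuss their allocation with the nurse or vascular technician.

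**Rank of the endpoint.** Section 6.1.2 lists microvascular function, in retina and skin, as secondary. The Primary Hypothesis in section 2 includes it as part b: "enhance microvascular function as estimated by retinal photos and skin heat-induced hyperemia".

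**The concern.** The trial places a device on the wrist in one arm only and measures a skin endpoint at the wrist in both. If the two sites coincide, prolonged strap contact could change local skin blood flow in a way unrelated to physical activity. Because this would happen mainly in the intervention arm and only after randomisation, neither randomisation nor adjustment for the baseline value would remove it. A difference in skin microvascular function could then be read as an effect of light activity when it came from the strap, or a real effect could be hidden. What is at stake is the interpretation of the skin measure, which is a named secondary endpoint and part of the stated hypothesis.

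**Working it through.** The plan gives no figure on this point, so the check is mainly a comparison of its sections.

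1. **Is the exposure confined to one arm?** For the trial device, yes (section 5.1).
2. **Can it reach the Doppler site?** The flowmotion probe is on the left wrist. The monitor's side is not given, so overlap is permitted but not established. Other sites in section 6.3 are specified: right carotid and right femoral for PWV, left carotid for ultrasound, right thigh for the activPAL and the non-dominant arm for blood sampling. The monitor is not.
3. **Does the visit-day rule close the gap?** Only partly. It takes the device off for the recording, but wear until the night before is compatible with both section 5.1 and section 6.2. No minimum interval or inspection of the probe site is stated.
4. **When does exposure start?** Section 3.2 puts randomisation after the baseline measurements, so baseline is free of it. Months 3 and 6 are exposed. The text does not say whether the monitor is kept after month 6, so month 12 is open.
5. **Which measures can a local effect reach?** Skin flowmotion, and heat-induced hyperaemia if the second probe is also at the left wrist. Retinal photographs, tonometry at the carotid and femoral arteries, and carotid ultrasound are taken elsewhere.

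**Scale, on assumptions only.** Let p_I and p_C be the proportions of intervention and control participants with a band recently at the probe site, and d the local effect in SD units. The artefact in the between-arm difference is then

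b = (p_I − p_C) × d.

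None of the three is in the documents. For b = 0.2 SD, for example, d must be 0.2 if p_I − p_C = 1, 0.4 if it is 0.5, and 0.8 if it is 0.25.

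With no true effect, n per arm and SE = √(2/n), the probability of a significant result at two-sided 0.05 is

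1 − Φ(1.96 − b/SE) + Φ(−1.96 − b/SE).

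Section 4.4 plans 80 per group with about 10% drop-out: 80 × 0.9 = 72. For n = 72, SE = √(2/72) = 0.1667. At b = 0.2, b/SE = 1.2, which gives 1 − Φ(0.76) + Φ(−3.16) = 0.224.

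| Assumed b (SD) | 72 per arm | 80 per arm |
|---|---|---|
| 0 | 5.0% | 5.0% |
| 0.1 | 9.2% | 9.7% |
| 0.2 | 22.4% | 24.4% |
| 0.3 | 43.7% | 47.5% |

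The table shows how sensitive a comparison of this size is to a one-arm shift. It does not estimate the shift in this trial.

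**The case against.** The case against has several parts.

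- **Nothing shows that an artefact exists.** No section says that a strap removed before the visit alters flowmotion or hyperaemia, and the table rests on assumed shifts. This stands: the point is an uncontrolled path to bias, not a demonstrated bias.
- **The protocol already removes the device on visit days.** True, and this covers the recording itself. It does not cover carry-over from the preceding days and nights.
- **Controls may wear their own watches.** Also true. Nothing in sections 4.2, 4.3 or 5.1 prevents it, so the contrast in strap exposure is p_I − p_C, not p_I alone.
- **The heating probe's site is not given.** Correct, so exposure of the hyperaemia measure named in the hypothesis is an inference.
- **Wearing side belongs in a working procedure.** Partly fair. But the side decides whether a one-arm exposure overlaps a trial measurement, and the protocol does specify sides for other measurements.

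A reader might go further and infer that the strap is tight, that exposure is fully confounded with arm, or that the assessor blind and the primary outcomes are compromised. The documents do not support these readings. The monitor is described only as being worn like a watch. Some intervention participants may use the right wrist. A strap mark does not identify allocation when controls may have one from their own watch. PWV and carotid distensibility are not measured at the wrist, and the ultrasound is read off-line and blinded. Unblinding through a mark remains a minor possibility.

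**Conclusion.** The point holds as a design gap of limited reach. As written, the plan allows the left-wrist Doppler site to be recently strapped skin after baseline, through the trial device, in the intervention arm only. The possible artefact concerns the skin microvascular endpoint, and its size and direction cannot be determined from the documents. The conclusion assumes that some intervention participants wear the monitor on the left and that recent wear can affect local skin flow; the protocol neither confirms nor excludes either. There is no contradiction or wrong figure here. The change is worth making because it removes the path almost without cost.

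**What to change.** - **Section 5.1:** instruct intervention participants to wear the monitor on the right wrist throughout.
- **Section 6.3, Microcirculation Measurements:** keep the Doppler probes on the left arm, state the heating probe's site, and ask participants in both arms to wear no watch or band on the left wrist for a stated period before each visit. Applying this to both arms also deals with controls' own watches.
- **Participants already enrolled:** record the wearing side and use it only for a descriptive sensitivity check. Excluding left-wrist wearers from the comparison would select on behaviour after randomisation, mostly in one arm.

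The cost is a line in the device instruction, a short addition to the measurement procedure, and slight inconvenience for people who prefer the left wrist. The change protects the Doppler site. It does not remove a visible strap mark, which would only move to the other wrist.
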